**Figure 1. Participant distribution by Session**

## Methods

The Cionic wearable devices measure information about leg and muscle activity that enable mobility. The system consists of four leg straps, two foot sensors, and two foot insoles (or pressure array of pressure sensors), connected by insulated wires to a battery-powered control box worn on the thigh. The device can also be (optionally) configured to attach sticky electrode pads to the body, which are connected to an integrated battery powered control box worn at the hip, capable of stimulating muscle contractions.

The Cionic sensing devices are made up of sensors that are either part of compression-type wearable garments held snugly in place with velcro and sticky electrode gel, or attached to the shoes. This system will measure what the body, i.e., pelvis and legs, are doing while the participant. It also has sensors that measure what some of the body's muscles are doing during movement. When muscles are working,

they produce a small electric current that can be measured with sensors on the skin over the muscle.

Each participant will be asked to wear:

- Two elastic leg straps (Figure 2), containing multiple sensors, will be secured to each leg with Velcro. One strap will be secured around each thigh and one around each shank (lower leg). These straps will measure two things: (1) the activity levels of the muscles underneath the straps, and (2) the physical orientation of the legs.
- One foot sensor will also attach to the top of the participant's shoes to measure the physical orientation of the feet. The straps and foot sensors will be connected by stretchable wires.
- Lastly, thin pressure-sensing pressure pads (Figure 3) will be inserted inside each of the shoes. The pressure sensors measure where the foot is applying downward pressure inside the shoes at all times.

Participants in sessions B and C will wear the Cionic stimulation device (Figure 4), which includes all of the above, as well as sticky electrode pads connected to a battery powered control box worn at the hip, capable of stimulating muscle contractions (manually or algorithmically).

- One Functional Electrical Stimulation (FES) control box clipped to the hip.
- Maximum of eight pairs (16 total) sticky electrode pads worn at one time on the shins, calves, quadriceps, and/or hamstrings. These electrodes will connect to the FES control box via insulated wires.

These devices connect wirelessly via Bluetooth to an application running on a smartphone. The smartphone's camera will also record video of the lower body only. We will not record the participant's face. The content of the data will be uploaded to a secure server and used to develop product algorithms and inform product design.

The Apollo system utilizes a battery-powered, body-worn electronic controller that generates stimulation waveforms and receives EMG signals. The magnitude, frequency and duration of the stimulation waveforms are controlled by a smartphone application

# CIONIC

operated by the study coordinator. Software, hardware, and user controls all limit the maximum energy that can be delivered to a subject. The controller's maximum output parameters (current of 100 mA, pulse duration of 400 microseconds) enable a maximum per-pulse charge of 40 microcoulombs, which is equivalent to our predicate device (Otto Bock, Stilwell Med4, K080950) which are cleared for the same indications intended for the Apollo system.

Each stimulation session starts with current amplitude at 0 mA and is increased manually by the study coordinator in small increments, preventing sudden, uncontrolled increases in energy. Recording of electromyography (EMG) signals from muscle in the Apollo system does not involve delivery of energy to the patient. Pain can occur when EMG is utilized for nerve conduction studies with needle electrodes, however this is not the paradigm used in our study.

The electronic controller is being developed in conformity with IEC 60601-2-10 (Medical Electrical Equipment - Particular requirements for the basic safety and essential performance of nerve and muscle stimulators).

While used for a different indication for use, an over-the-counter transcutaneous electrical nerve stimulator, commonly referred to as a TENS Device, is well adopted therapy that can be used as a commonly recognized example of how the electrical stimulation will feel on the study participant.

**Figure 2. Apollo system leg straps**

**Figure 3. Representative foot sensors (image source: TekScan.com**

**Figure 4. Apollo system control unit**

## **Data Collection and Movement Tasks by Session**

Each independent session of the study involves directing the participant to perform a series of movement tasks in order to elicit different types of data. Each session is subdivided into tasks. Instruction will be provided to the participant before entering a new task, and the study coordinator will also use these opportunities to gauge participant pain, need for breaks and understanding of the task. For pediatric participants, their parent or guardian will also be consulted between tasks.

### **Session A - Sensor Data Collection**

Session A will consist of approximately 2 hours of sensor data collection. The participant will be outfitted with a Cionic leg straps on the thigh and shank of both legs and foot pressure sensors taped under both shoes. The leg straps consist of EMG (non-invasive muscle electrical signals) sensors and IMU (accelerometry/movement signals) sensors. Participants will be asked to wear clothing amenable to sensor placement and movement such as shorts.

## Task 1: Introduction and anatomical measurements

- Introductions to all Cionic team members and review study activities.
- Confirm signed informed consent.
- Provide opportunity for participants to change clothes if necessary.
- Measure anatomical features using a flexible tape including thigh and calf circumference and leg length.

## Task 2: Equipment setup

- Secure leg straps to the participant's body and confirm comfort.
- Initiate data collection device and ensure connection to Smartphone app.
- Record non-personally identifiable participant information within the app.
- Validate system operation by confirming communication between app and all data collection channels.
- Sensors will be calibrated by guiding the participant through specific limb movements both standing and sitting.

## Task 3: Treadmill

- Participant will be guided onto a treadmill with side handles.
- An overhead safety harness will be fitted to any participant who requires or requests a harness.
- Walking will be initiated on the treadmill at a rate no more than the participant's comfort level for up to 5 minutes while movement data is collected.
- The process will then be repeated up to 5 times for walking intervals of up to 2 minutes while data is collected and reviewed.
- Verbal check-in with participants for pain, understanding and need for a break.

## Task 4: Overground Gait

- Participant will be guided to an open area with at least 20 feet of walking area without any physical obstructions.
- Participant will be asked to walk unaided in the walking area for up to 5 minutes while data is collected.
- The process will then be repeated up to 5 times for walking intervals of up to 2 minutes while data is collected and reviewed.
- Verbal check-in with participant for pain, understanding and need for a break.

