### AIM 1 - Movement measurement

Session A of the study is designed to collect physiological data on impacted participant populations in order to record and characterize movement from people with lower body deficits. This will be accomplished by recording kinematic data (movement velocity, range of motion) and functional data (muscle activation signals via electromyography (EMG). The output of this session will be data recorded from the system which is de-identified and used for internal Cionic engineering and software development. This Session does not involve electrical stimulation.

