**Table 1. Summary of protocol session**

	Session A	Session B	Session C
Specific Aim	Movement measurement	Muscle activation & usability	FES for Gait Assistance
Involves data collection?	Yes	Yes	Yes
Involves stimulation?	No	Yes	Yes
Approximate # of adult participants	20	20	10
Approximate # of pediatric participants	10	10	10
Activity	Measure movement during walking without any intervention.	Measure muscle activity and effect of FES on muscles only (no movement).	Measure effect of FES on gait.

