### Inclusion criteria

[figure not shown]
- Are living with lower extremity impairment that makes walking difficult and/or uncomfortable
- Capable of sitting, standing and walking with or without assistance
- Ability to walk at least 10 meters with minimal assistance

[figure not shown]
- Ability to understand and follow the basic instructions in English
- Parent/guardian must be accompany and be present with pediatric participants

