## Risk Mitigation Strategies

Cionic has done the following things to reduce the risks to participants.

- Have done internal experiments and made design modifications to increase safety
- Cionic team is well trained and to strictly follow the study protocols
- Participants will have the option to wear a safety harness secured overhead to protect them from falls. Session C will require all participants to be in harness.
- The testing area will be safe, well lit and clear of all obstacles
- Any actions will be discussed with the participant prior and their comfort will be monitored throughout the study
- Participants will self manage a walking speed and control their level of electrical stimulation for their own comfort level
- A COVID safety protocol will be strictly adhered to, requiring all people who visit the site to check temperatures, practice social distancing, require mask

wearing and follow all other CDC guidelines to prevent the spread of COVID-19

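### Session A Task 4 asks participants to walk overground unaided, with no exception, although eligibility admits people who walk with assistance

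*Protocol*

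**What the plan says.** Protocol, Session A, Task 4 (Overground Gait), instructs: "Participant will be asked to walk unaided in the walking area for up to 5 minutes while data is collected". The bout may then be repeated up to five times, for up to two minutes each. The task text has no alternative for someone who walks with a cane, walker, orthosis or helper. The word unaided occurs nowhere else in the protocol or SAP.

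Protocol, Inclusion criteria, requires that participants be "Capable of sitting, standing and walking with or without assistance" and sets the distance requirement as "Ability to walk at least 10 meters with minimal assistance". These criteria apply to all three sessions. Nothing visible there or under Exclusion criteria requires independent walking.

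Table 1 summarises the activity of Session A as "Measure movement during walking without any intervention", and Aim 1 adds: "This Session does not involve electrical stimulation".

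On safety, Risk Mitigation Strategies states: "Participants will have the option to wear a safety harness secured overhead to protect them from falls". Task 3 (Treadmill) says how this works there: "An overhead safety harness will be fitted to any participant who requires or requests a harness". Task 4 does not mention a harness.

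**The concern.** The people admitted and the task they are given do not quite match. Someone can meet every visible criterion by walking ten metres with some help, enter Session A, and then be asked to walk overground without that help. Falls are among the risks the protocol itself lists under Risk & Benefit Assessment, and the population is defined by difficulty in walking.

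Two things are at stake. One is an avoidable fall risk for any participant who depends on an aid. The other is consistent conduct: coordinators who read the word differently would run the task differently, and the protocol gives them nothing to settle it.

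**Working it through.** The plan gives no figure to reproduce on this point, so the check is a comparison of text with two small sums.

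**1. Instruction against eligibility.** Task 4 addresses the Session A participant without qualification. The inclusion criteria expressly accept walking with assistance and set the distance requirement at minimal assistance. No visible text adds a Session A requirement of independent walking, sends aid users to another session, or exempts them from Task 4. An eligible aid user can therefore reach Task 4 with no instruction other than to walk unaided.

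**2. Possible meanings of the word.**
- *Without stimulation.* This would remove the mismatch. Elsewhere the protocol does use the language of assistance for stimulation, and Table 1 describes Session A as free of intervention. But the whole session is unstimulated, and Task 3, equally unstimulated, does not use the word. On this reading it would add nothing to Task 4.
- *Without the handles and harness of Task 3.* This is plausible, because Task 4 follows directly. It is not stated, and it would still leave open what an aid user should do.
- *Without any walking aid or helper.* This is the ordinary meaning, and recording unsupported gait would suit Aim 1. It then needs a limit to people who can do it safely, and none is given.

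**3. Safeguards.** The protocol screens candidates by video call for safe walking, gauges pain, understanding and need for breaks before each new task, consults parents, lets participants set their own pace, offers a harness and allows withdrawal. A person who walks safely with a cane can pass the screen. The other measures mostly depend on the participant speaking up after being asked. None says what an aid user does in Task 4.

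**4. Extent.**
- Maximum overground walking in Task 4: 5 + 5 × 2 = 15 minutes. There is no minimum.
- Planned Session A participants: 20 adults + 10 children = about 30.
- Share who rely on an aid: not given. The number affected could be anything from 0 to about 30, and no estimate is made.

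**5. Link to the analysis.** The protocol's Statistical Analysis section foresees at most averages and their spread, with no inference. The SAP compares stimulated with unstimulated walking in the same person. Session A has no stimulation, so its participants cannot supply such a pair from that session.

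**The case against.** The strongest reply is that the criteria serve three independent sessions. Participant Selection counts up to 50 different adults (20 + 20 + 10) and 30 different children (10 + 10 + 10). Table 1 describes Session B as involving no movement, and Session C walking takes place on a treadmill with handles and a compulsory harness. Accepting assisted walkers makes sense for those sessions, and eligibility that is broader than one task is not in itself a contradiction. This stands, and it weakens the point. It does not remove it, because no rule allocates aid users away from Session A.

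Second, benign meanings of the word exist, and unsupported gait would be a legitimate thing to record. That also stands, but the protocol does not say which meaning applies.

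Third, the safeguards cover much of the risk. The line "Cionic team is well trained and to strictly follow the study protocols" cuts both ways: it favours a literal reading of Task 4, and it equally binds staff to the protective measures in the same list.

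Fourth, some of the inclusion list and the screening script cannot be seen. The point therefore rests on the visible criteria, which expressly admit assisted walkers.

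A reader might go further and infer that the 15-minute ceiling set against the 10-metre entry requirement measures the added danger. It does not: one is a maximum time that participants may cut short, the other a minimum distance for entry. A reader might also infer that the pooled gait averages are biased or that the SAP's comparison is compromised. The documents do not support either: the averages are optional and descriptive, lower-body video may already show an aid, and the SAP's paired test does not draw on Session A walking.

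**Conclusion.** The point holds as a minor matter of safety and clarity. As written, Task 4 asks some eligible participants to walk without support they may need, and nothing in the documents exempts them. Existing safeguards reduce the resulting fall risk but do not remove it.

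The size cannot be stated, because the number of aid users among the roughly 30 Session A participants is unknown and could be zero. The conclusion assumes that the word carries its ordinary meaning and that no criterion lost from the visible text requires independent walking. It would fall away if the sponsor meant only the absence of stimulation and staff were told so. No pooled estimate, power figure or SAP test is affected.

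**What to change.** Reword Task 4 so that unaided walking is limited to participants who can walk safely without an aid, and everyone else uses their usual aid or minimal assistance. Record the aid used for each bout. The note is needed because the rewording openly allows both kinds of walking; the video and the mobility rating already collected may cover part of it.

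The cost is one sentence in the protocol and one short entry per participant. The downside is that some overground data will be aided gait, so the descriptive sample is slightly more mixed. For a study that seeks to characterise movement in people with lower-limb deficits, that is a small price.

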## Task 5: Seated Exercises

- Participant will be seated comfortably.
- Participants will be asked to perform isolated leg movements. Movements will include knee flexion and extension, hip abduction and adduction, thigh flexion and extension
- Each movement may be repeated up to 5 times.
- Verbal check-in with participant for pain, understanding and need for a break.

After completion of all tasks, equipment will be removed from the participant and sanitized with isopropyl alcohol. A brief post-study survey will be administered verbally or via computer by the study coordinator.

## **Session B - FES Pad Calibration**

Session B will consist of ~2 hours of FES stimulation on the participant's muscles while sensor measurements are made. The goal is to test the placement of our FES pads on each of the 4 main muscle groups: quadriceps, hamstrings, calf, and tibialis anterior (front of lower leg). The participant will wear sensorized leg straps equipped with FES and two foot pressure sensors inside each shoe. Surface muscle stimulation will be applied gently at first, increasing slowly as directed by the participant. Several electrode pad locations will be tested for each muscle.

## Task 1: Introduction and anatomical measurements

- Introductions to all Cionic team members and review study activities
- Confirm signed informed consent
- Provide opportunity for participants to change clothes if necessary
- Measure anatomical features using a flexible tape including thigh and calf circumference and leg length.

## Task 2: Equipment setup

- Secure leg straps to participant's body and confirm comfort.
- Initiate data collection device and ensure connection to Smartphone app.
- Record non-personally identifiable participant information within the app.

- Validate system operation by confirming communication between app and all data collection channels.
- Sensors will be calibrated by guiding the participant through specific limb movements both standing and sitting.

#### Task 4: Isolated muscle group data collection

- An array of 2" x 2" adhesive electrodes (typical of TENS therapy system) will be applied to a muscle group of interest.
- Sensors will be calibrated by guiding the participant through specific limb movements both standing and sitting.
- Participants will be asked to move their feet and legs to access their range of motion
- Stimulation will be delivered to different combinations of electrodes on the muscle group. At each instance stimulation will be started at the lowest setting (0mA) and increased slowly until either a sufficient muscle response is achieved or the participant reports discomfort. If any discomfort is felt, stimulation will be immediately stopped, and a new combination of electrodes will be selected.
- Verbal check-in with participant for pain, understanding and need for a break.

Muscle Group	Tibialis Anterior	Quadriceps	Gastrocnemius	Hamstrings
Participant position	Supine	Seated	Prone	Prone
Intended Movement	Foot dorsiflexion	Lower leg extension	Foot plantar flexion	Lower leg flexion

After completion of all tasks, equipment will be removed from the participant and sanitized with isopropyl alcohol. A brief post-study survey will be administered verbally or via computer by the study coordinator.

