### Exclusion criteria

- Having non-reversal damage to the central and peripheral body's system
- Underlying pre-existing conditions like thrombosis/hemorrhage, severe epilepsy or other seizure disorder, severe atrophy or history of implanted electrical devices
- Cognitive impairment that would prevent the participant from fully understanding the study and ability to provide informed consent
- Lower motor neuron disease or injury that may impair response to stimulation
- Pregnant woman
- Skin conditions of the affected lower limb, including cuts, burns or lesions
- Latex allergy

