## **Session C - FES Gait Assist**

Session C will consist of approximately 2 hours of periodic FES stimulation while the participant walks. The goal is to test Cionic's gait augmentation stimulation algorithms. The participant will wear sensorized leg straps equipped with FES and foot pressure sensors inside each shoe. Surface muscle stimulation will be applied gently at first, increasing slowly as directed by the participant.

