## Task 4: Treadmill trial with stimulation assist

- Participant remains on the treadmill with side handles.
- An overhead safety harness remains fitted to the participant.
- A gait assist algorithm will be entered into the Apollo system.
- Walking will be initiated on the treadmill at a rate no more than the participant's comfort level
- After notifying participant, the electrical stimulation algorithm will be applied to the leg electrodes, starting at 0mA and slowly increased until effective gait is achieved or the participant reports discomfort. If pain or discomfort is reported the stimulation and treadmill will be stopped immediately.
- The process may be repeated up to 10 times with different gait assist algorithms.
- Verbal check-in with participant for pain, understanding and need for a break.

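### In Session B Task 4 and Session C Task 4 the discomfort stop depends on the leg being able to feel, and no visible step checks leg sensation before stimulation.

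*Protocol*

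**What the plan says.** The protocol describes two ramps that end on a response or on reported discomfort.

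- Session B, Task 4 (isolated muscle group data collection): from 0 mA, the current is "increased slowly until either a sufficient muscle response is achieved or the participant reports discomfort". Any discomfort ends that attempt, and another electrode combination is tried.
- Session C, Task 4 (treadmill trial with stimulation assist): from 0 mA, it is "slowly increased until effective gait is achieved or the participant reports discomfort". Pain or discomfort stops both the stimulation and the treadmill.

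The participant has a part in both. The Session B introduction says "Surface muscle stimulation will be applied gently at first, increasing slowly as directed by the participant", and the Session C introduction repeats "increasing slowly as directed by the participant". Under Methods, the study coordinator operates the controls and raises the current by hand in small steps. The documents do not say who decides that a muscle response is sufficient or that gait is effective.

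Entry is broad: "Are living with lower extremity impairment that makes walking difficult and/or uncomfortable". The exclusions closest to this point are:
- a general one for lasting central and peripheral damage;
- "Lower motor neuron disease or injury that may impair response to stimulation";
- "severe atrophy or history of implanted electrical devices";
- damaged skin on the affected leg.

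None of them names sensation.

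**The concern.** A stop that waits for the participant to report discomfort works only if the participant can feel the stimulated area. The population makes this a fair question. The protocol's Benefits section speaks of neurological injuries and conditions, and the SAP's Power Analysis takes its effect size from post-stroke participants. Some people with such conditions may have reduced feeling in the leg.

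Reduced feeling alone does not defeat the ramp, because a good motor response still ends it. The gap opens where an area is poorly felt and also responds poorly. In Session B some poor responses are to be expected, since "Several electrode pad locations will be tested for each muscle" and the aim is to learn which placements work. In Session C a muscle may contract without gait becoming effective, and the process may be repeated up to 10 times with different algorithms.

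What is at stake is participant safety. The point has no bearing on the SAP's comparison of stimulated with unstimulated gait.

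**Working it through.** **1. Who is stimulated (Protocol, Table 1).** Session B: 20 adults + 10 children = 30. Session C: 10 + 10 = 20. Total 30 + 20 = 50, of whom 10 + 10 = 20 are children. Session A, without stimulation, adds 20 + 10 = 30. The sum 50 + 30 = 80 agrees with the 50 adults and 30 children under Participant Selection, so the sessions are counted as different people.

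**2. The device ceiling (Protocol, Methods).** Charge per pulse = current × pulse duration = 100 mA × 400 microseconds = 0.1 A × 0.0004 s = 0.00004 C = 40 microcoulombs. This reproduces the stated figure. The ceiling applies to the whole device; no lower limit is stated for an area with reduced feeling.

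**3. Which safeguards need feeling in the leg.**

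| Safeguard | Where in the protocol | Depends on feeling? |
|---|---|---|
| Stop on reported discomfort | Task 4, Sessions B and C | Yes |
| Verbal pain check-ins | Task 4, Sessions B and C | Yes |
| Participant directs the increase | Introductions to Sessions B and C | Largely; no basis is stated |
| Participant controls the level | Risk Mitigation Strategies | Yes; it is tied to comfort |
| Stop on sufficient response or effective gait | Task 4, Sessions B and C | No, but it may not be reached |
| 0 mA start, small manual steps | Methods | No |
| Software, hardware and user limits | Methods | No |

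**4. Where a sensation check could stand.**
- Inclusion criteria: impairment, walking ability, English instructions, a guardian's presence. Two figures in this list are not shown.
- Exclusion criteria: the general damage exclusion may remove some people with sensory loss, but it names no way of checking. Read literally, it also sits awkwardly with a population recruited for impaired walking. The lower motor neuron exclusion concerns response to stimulation.
- Screening call (Participant Identification, Recruitment & Informed Consent): safe walking and comprehension. The screener and the script are not in the documents.
- Set-up (Tasks 1 and 2, Sessions B and C): tape measurements, strap comfort, connectivity and sensor calibration.
- Session B: the visible text goes from Task 2 to Task 4, so the content of any Task 3 is unknown.
- Session B, Task 4: range of motion before stimulation.

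No visible step asks about touch.

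**5. Time to ask.** The Session B table names 4 muscle groups, so there are 4 areas on one leg or 8 on both; Methods allows at most eight electrode pairs at once. At an assumed 10 seconds each, 4 × 10 = 40 s and 8 × 10 = 80 s. Asking separately at an assumed 3 pad locations per muscle on both legs takes 8 × 3 × 10 = 240 s, or 4 minutes. As shares, 40 / 7,200 = 0.6% of a 2-hour session, and 240 / 5,400 = 4.4% of the 1.5-hour pediatric target.

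**The case against.** The strongest reply is that the gap may not exist. A sensation question would naturally sit in the screener or the call script, and neither is visible. The general damage exclusion may already remove some of the people in question. This stands, and it is why confidence is low.

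Second, the exposed group may be very small. It needs reduced feeling and a poor response in the same area, in people who can walk 10 meters, after the lower motor neuron, severe atrophy and skin exclusions. The ramp is gradual, and the output ceiling is described as equivalent to a cleared predicate. The only skin harm listed under Risk & Benefit Assessment is minor irritation. This also stands and limits the weight of the point.

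Third, irritation has other routes to notice. Adverse events are recorded for each participant and reviewed by the investigator within one business day, and each session ends with a debriefing and exit interview. These are real, but they come after stimulation and rely largely on the participant noticing something. They do not replace a check beforehand.

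Fourth, nothing in the documents shows that a light-touch answer predicts whether current will be felt as uncomfortable. That is fair. The question is a simple first check and has not been shown to be a validated test.

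A reader might go further and infer that staff alone push the current until they are satisfied. The documents do not support this: the participant directs the increase, and nobody is named as judge of the response. Nor does the point reach all stimulation in Session C. Task 5 uses low stimulation tuned on participant feedback and is not a ramp of this kind.

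**Conclusion.** The point holds in a limited form. On the visible text, the participant-side safeguards in the two Task 4 ramps assume a leg that can feel, and nothing visible confirms it. The number exposed cannot be calculated, because the documents give no prevalence of reduced sensation. It would be wrong to read all 50 stimulated participants as at risk; 50 is the number who would be asked. It would also be wrong to conclude that participants would be harmed at the device maximum, since the documents give no evidence of injury at that output.

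The conclusion rests on two assumptions: that the unseen screening material and any Session B Task 3 contain no sensation item, and that some enrolled participants have reduced feeling in the leg. If the first is wrong, the sponsor can close the point by citing the item. This is a cheap safety improvement to consider, held with low confidence.

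**What to change.** Before stimulation in Sessions B and C, ask and record for each area to be stimulated whether light touch feels normal, reduced or absent.

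- Normal: proceed as planned.
- Absent: do not stimulate that area.
- Reduced: skip the area; or, if it is stimulated, do not rely on reported discomfort as the stop, and look at the skin when the pads are removed.

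Skipping is the simpler choice for a reduced area. The documents give no basis for a lower current limit at such sites, so none is proposed.

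The cost is one short question per area, plus a skin check only at areas with reduced feeling that are stimulated. A few skipped areas would mean slightly less electrode placement data in Session B, and possibly fewer areas assisted in Session C.
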